3.4.1.1. Primary Endpoints

- Incidence of MAAEs and SAEs through 1 week post final vaccine administration
- Incidence of MAAEs and SAEs through 30 days post final vaccine administration
- Incidence of MAAEs and SAEs through 6 months post final vaccine administration
- Incidence and severity of solicited local reactogenicity AEs through 1 week after each vaccine administration
- Incidence and severity of solicited systemic reactogenicity AEs through 1 week after each vaccine administration
- Incidence and severity of unsolicited AEs through 1 week post final vaccine administration

- Incidence and severity of unsolicited AEs through 30 days post final vaccine administration
- Incidence of abnormal changes of laboratory safety examinations
- Changes in vital signs

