6.3.1. Solicited Local and Systemic Adverse Events

Solicited AEs will be captured at study visits and by a diary distributed to participants. Thermometers and rulers will be provided to participants for evaluating AEs. Text and/or phone reminders to complete the solicited AE diary may be provided to participants.

Solicited local AEs to be assessed include redness, firmness, swelling, pain or itching at the injection site, medication taken for pain after IM administration, tingling/numbness, and bleeding or bruising at the injection site after IM administration. Solicited systemic AEs to be assessed include chills, nausea, vomiting, diarrhea, headache, fatigue, myalgia, abdominal discomfort/pain, joint pain, and fever. The solicited AE diary may be either electronic diary (eDiary) or a paper diary, as available. A sample diary for collecting solicited AEs is provided in [Appendix 1](#).

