Fever (°C) ** (°F) **	38.0 – 38.4 100.4 – 101.1	38.5 – 38.9 101.2 – 102.0	39.0 – 40 102.1 – 104	> 40 > 104
Tachycardia - beats per minute	101 – 115	116 – 130	> 130	ER visit or hospitalization for arrhythmia
Bradycardia - beats per minute***	50 – 54	45 – 49	< 45	ER visit or hospitalization for arrhythmia
Hypertension (systolic) - mm Hg	141 – 150	151 – 155	> 155	ER visit or hospitalization for malignant hypertension
Hypertension (diastolic) - mm Hg	91 – 95	96 – 100	> 100	ER visit or hospitalization for malignant hypertension
Hypotension (systolic) – mm Hg	85 – 89	80 – 84	< 80	ER visit or hospitalization for hypotensive shock
Respiratory Rate – breaths per minute	17 – 20	21 – 25	> 25	Intubation

* Participant should be at rest for all vital sign measurements.

** Oral temperature; no recent hot or cold beverages or smoking.

*** When resting heart rate is between 60 – 100 beats per minute. Use clinical judgement when characterizing bradycardia among some healthy participant populations, for example, conditioned athletes.

Table 13: Clinical Abnormalities: Systemic

Systemic (General)	Mild (Grade 1)	Moderate (Grade 2)	Severe (Grade 3)	Potentially Life Threatening (Grade 4)
Nausea/vomiting	No interference with activity or 1 – 2 episodes/24 hours	Some interference with activity or > 2 episodes/24 hours	Prevents daily activity, requires outpatient IV hydration	ER visit or hospitalization for hypotensive shock
Diarrhea	2 – 3 loose stools or < 400 gms/24 hours	4 – 5 stools or 400 – 800 gms/24 hours	6 or more watery stools or > 800 gms/24 hours or requires outpatient IV hydration	ER visit or hospitalization
Headache	No interference with activity	Repeated use of non-narcotic pain reliever > 24 hours or some interference with activity	Significant; any use of narcotic pain reliever or prevents daily activity	ER visit or hospitalization
Fatigue	No interference with activity	Some interference with activity	Significant; prevents daily activity	ER visit or hospitalization
Myalgia	No interference with activity	Some interference with activity	Significant; prevents daily activity	ER visit or hospitalization
Systemic Illness	Mild (Grade 1)	(Moderate(Grade 2)	Severe (Grade 3)	Potentially Life Threatening (Grade 4)
Illness or clinical adverse event (as defined according to applicable regulations)	No interference with activity	Some interference with activity not requiring medical intervention	Prevents daily activity and requires medical intervention	ER visit or hospitalization

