7.8.2. Phase 1 Study Toxicity Study Stopping Rules

Safety will be monitored throughout the study.

In the phase 1 study, the first 7 days after vaccine administration are defined as the toxicity assessment period. The SRC will also review each treatment-related SAE and toxicity, during the toxicity assessment period and each treatment-related SAE and grade ≥ 3 AE after the toxicity assessment period, to determine if the event warrants stopping the trial, modifying the trial, or continuing without modification. In the event of a death that is suspected to be related to the treatment regimen, further enrollment will be delayed until the SRC approves continuation of enrollment in order to allow for proper review and notification to the IRB and the SAHPRA. In the event of a pause in clinical trial enrollment due to toxicity, both the SRC and the SAHPRA will be notified.

Stopping/pausing guidelines are predefined criteria that halt the conduct of a study. Toxicities that may warrant stopping of the trial, based on SAHPRA guidance and with grading scales from the Guidance for Industry: Toxicity Grading Scale for Healthy Adult and Adolescent Volunteers Enrolled in Preventive Vaccine Clinical Trials (2007) (see [Section 7.1](#)), include the following:

1. If 1 or more participants experience a Grade 4 AE ([Section 7.1](#)), vital sign or laboratory abnormality that is judged related to study vaccine, all vaccinations will be suspended until a full safety review is performed.
2. If 3 or more participants report the same or similar Grade 3 solicited AE, unsolicited AE, or clinically relevant laboratory abnormality judged related to the study vaccine, all vaccinations will be suspended until a full safety review is performed.
3. The study will be halted (no new enrollments and no further investigational product administered until a full safety review and consultation with the health authorities completed) if one of the following occurs:
 - a. One participant experiences an SAE judged related to the study vaccine, or
 - b. There is a participant death judged related to the study vaccine.

If any of the halting rules are met, vaccination of participants will be suspended until after full review of safety data by the SRC. The Investigator must inform the Sponsor and IRB if any of the halting rules are met. The Sponsor then must inform the SRC and SAHPRA.

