8. Is there bruising at the injection site?	Check:  Yes or  No	 Yes or  No	 Yes or  No	 Yes or  No	 Yes or  No	 Yes or  No	 Yes or  No	 Yes or  No

Grading Injection Site Pain or Itching:

Mild – Noticeable, does not interfere with activity

Moderate – Interferes with activity, limiting activities of daily life

Severe – Severely limiting self-care activities of daily living, incapacitating

STUDY NUMBER*: _____

Patient Number*		Date of Vaccine Administration	/	/	/	*To be completed by the site		
-----------------	--	--------------------------------	---	---	---	------------------------------	--	--

Please answer all questions below daily for 7 days, beginning with day of treatment. Be sure to bring back this completed diary to your next clinic visit.

| Solicited systemic AEs | Instructions | Date / / |
|---|---|---|---|---|---|---|---|---|
| 1. Have you experienced any chills? | Check:
 Yes or  No
If yes, tell us if the chills are mild, moderate or severe |  Yes or  No
Mild
Moderate
Severe |
| 2. Have you experienced nausea? | Check:
 Yes or  No
If yes, tell us if the nausea is mild, moderate or severe |  Yes or  No
Mild
Moderate
Severe |
| 3. Have you experienced vomiting? | Check:
 Yes or  No
If yes, tell us if the vomiting is mild, moderate or severe |  Yes or  No
Mild
Moderate
Severe |
| 4. Have you experienced diarrhea? | Check:
 Yes or  No
If yes, tell us if the diarrhea is mild, moderate or severe |  Yes or  No
Mild
Moderate
Severe |
| 5. Have you experienced any headache? | Check:
 Yes or  No
If yes, tell us if the headache is mild, moderate or severe |  Yes or  No
Mild
Moderate
Severe |

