| 6. Have you experienced any fatigue? | Check:
 Yes or  No
If yes, tell us if the fatigue is mild, moderate or severe |  Yes or  No
Mild
Moderate
Severe |
| 7. Have you experienced any muscle pain? | Check:
 Yes or  No
If yes, tell us if the muscle pain is mild, moderate or severe |  Yes or  No
Mild
Moderate
Severe |
| 8. Have you experienced any abdominal discomfort/pain? | Check:
 Yes or  No
If yes, tell us if the abdominal discomfort/pain is mild, moderate or severe |  Yes or  No
Mild
Moderate
Severe |
| 9. Have you experienced any joint pain? | Check:
 Yes or  No
If yes, tell us if the joint pain is mild, moderate or severe |  Yes or  No
Mild
Moderate
Severe |

STUDY NUMBER*:

| Solicited systemic AEs | Instructions | Date / / |
|---|---|---------------------------------------|---------------------------------------|---------------------------------------|---------------------------------------|---------------------------------------|---------------------------------------|---------------------------------------|
| 10. Record your daily temperature upon waking (do not drink anything 5 minutes before taking your temperature) | Fill in the temperature and time:
If your temperature is 38°C for more than 24 hours, call your doctor | ____ °C
Time:
____ :
AM / PM |

Grading Chills:

Mild: Mild sensation of cold, shivering, chattering of teeth
 Moderate: Moderate tremor of entire body, medication taken
 Severe: Prolonged or severe, does not respond to medication

Grading Nausea and Vomiting:

Mild: No interference with activity or 1 – 2 episodes/24 hours
 Moderate: Some interference with activity or > 2 episodes/24 hours
 Severe: Prevents daily activity, requires outpatient IV hydration

Grading Diarrhea:

Mild: 2 – 3 loose stools or < 400 gms/24 hours
 Moderate: 4 – 5 stools or 400 – 800 gms/24 hours
 Severe: 6 or more watery stools or > 800 gms/24 hours or requires outpatient IV hydration

Grading Headache:

Mild: No interference with activity
 Moderate: Repeated use of non-narcotic pain reliever > 24 hours or some interference with activity

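### The sample diary schedules one temperature a day, on waking, so it gives no valid post-vaccination reading on the treatment day and can miss or under-grade short fevers

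*Combined protocol and SAP*

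**What the plan says.** Section 6.3.1 lists fever among the solicited systemic events ("myalgia, abdominal discomfort/pain, joint pain, and fever"). Table 12 in section 7.1 grades it by temperature alone, with Grade 1 at "38.0 – 38.4 100.4 – 101.1" (°C, then °F). Section 3.4.1.1 makes these events a phase 1 primary endpoint: "Incidence and severity of solicited systemic reactogenicity AEs through 1 week after each vaccine administration". Section 3.4.2.2.1 repeats this as a phase 2 secondary endpoint. Grades also enter the phase 1 suspension criteria. Section 7.8.2 has a rule that begins "If 3 or more participants report the same or similar Grade 3 solicited AE" and another for related Grade 4 events, and section 7.8.2.1 counts related events of Grade 3 or above.

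Home measurement is described in two places. Section 6.3.1 says "Thermometers and rulers will be provided to participants for evaluating AEs". Appendix 1, systemic item 10, says "Record your daily temperature upon waking (do not drink anything 5 minutes before taking your temperature" and provides one temperature field and one time field per date. The page instruction is "Please answer all questions below daily for 7 days, beginning with day of treatment". Item 10 also carries a contact prompt: "If your temperature is 38°C for more than 24 hours, call your doctor". Table 10 places diary training at the day 1 visit.

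**The concern.** The endpoint concerns fever occurring, and its severity, over the week after each vaccination. The diary samples temperature at one fixed moment a day, and on the first date that moment falls before the vaccine. Systemic items 1 to 9 ask whether a symptom has been experienced, so they can cover the whole day. Item 10 is the only point measurement. It has no yes/no question, no daily maximum and no prompt to measure when feverish.

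At stake are the fever counts and grades in the solicited-event tables, and the fever component of the Grade 3 and Grade 4 counts seen by the Safety Review Committee after each ten-person phase 1 cohort. Any error from this source runs one way, towards fewer and milder fevers.

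**Working it through.** The plan states no fever rate, onset time or duration, and section 8.4 gives no statistical basis for the sample size, so there is no figure to reproduce. The check is a count of readings plus labelled illustrations.

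**1. Post-dose readings per vaccination.** There are seven diary dates, the first being the treatment day. Waking on that day precedes the dose. Valid post-dose waking readings = 7 − 1 = 6 (days 2 to 7). The treatment-day box would be pre-dose, blank, or filled later against the instruction. None of these is a defined post-vaccination reading.

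**2. Time to the first scheduled post-dose reading.** Gap = 24 − dose clock time + next waking time. Assume dosing between 08:00 and 16:00 and waking between 05:00 and 08:00 (neither is in the protocol).
- Shortest: 24 − 16 + 5 = 13 h.
- Longest: 24 − 8 + 8 = 24 h.

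**3. Chance that a reading falls within a fever of d hours.** With one reading every 24 h and uniformly distributed onset (assumed), this is min(1, d/24).
- 6 h: 6/24 = 0.25
- 12 h: 12/24 = 0.50
- 18 h: 18/24 = 0.75
- 24 h or longer: 1.00

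This is the chance of detecting the fever at all. The chance of measuring its peak grade is no higher.

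**4. Effect of an evening reading under the same model.** Moving the single reading from morning to evening leaves min(1, d/24) unchanged on the later days. Adding a second reading, taken as 12 h from the first (assumed), gives min(1, d/12): 6/12 = 0.50 for 6 h and 12/12 = 1.00 for 12 h.

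**5. Other routes of capture.**
- Clinic observation after each dose lasts 30 minutes (section 5.1.5).
- Temperature is taken at each visit, but the scheduled visits around the first diary week are days 1 and 8.
- Phase 2 arm 3 has a second dose on day 29. The next contact is a telephone call on day 36, and that diary is collected on day 60 (Table 10, footnotes f and g).
- Section 6.3.1 also allows solicited events to be captured at visits, so a recalled fever can be recorded.
- Appendix 2 asks only for symptoms not covered by the other diaries, so it does not invite fever reports.

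None of these supplies scheduled temperatures on the treatment evening or later in the day on days 2 to 7.

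**6. How under-capture passes into a count of three.** Take a cohort of 10 and a true Grade 3 fever rate of 30% (assumed). The binomial probability of observing three or more is 0.617 with full capture, 0.180 with 50% capture (10 participants at 0.15) and 0.034 with 25% capture (10 participants at 0.075). At a true rate of 20% the figures are 0.322, 0.070 and 0.012. This isolates fever within one cohort. The section 7.8.2 rule has no cohort limit, and section 7.8.2.1 counts any related event of Grade 3 or above, so these are not operating characteristics of the actual criteria.

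**The case against.** Appendix 1 is labelled a sample, section 6.3.1 allows an electronic diary, and the operative form may differ. That limits certainty about practice, but the protocol text sets no other home temperature schedule.

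A reader might infer that one reading in seven is a pre-dose value. The documents do not establish this. If thermometer and diary are handed over at the day 1 visit, a study reading on waking that day is impossible and the box may be blank. The time field would also let a participant enter a later reading. What stands is that no valid post-dose reading is defined for that day.

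A reader might also infer that fevers arising later in the day are lost altogether. They are not. A fever still present at the next waking is recorded, one reported at a visit can be captured, and hospital or emergency attendance would be recorded as a medically attended event. Chills, headache, fatigue and myalgia are asked about with no time-of-day limit. Other signals of a severe fever therefore exist, but Table 12 grades need a temperature.

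Nor does the contact prompt contradict Table 12. It is not a grading rule, and its 38°C is the Grade 1 lower bound. The remaining difficulty is narrower: a duration of more than 24 hours is hard to judge from one reading a day.

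Finally, fever is one of ten solicited systemic events, analyses are descriptive, the same diary appears to serve every cohort and arm, and no stated dose-selection rule is keyed to fever. All of this is fair and limits the consequence. It does not remove the downward bias.

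**Conclusion.** The point holds in limited form. Followed as written, the sample diary gives six post-vaccination waking temperatures and none on the treatment day. It does not prompt for fevers that begin and end between wakings, and it may understate the peak of others. Fever incidence and grade are biased downwards within the two solicited systemic endpoints and in the Grade 3 and 4 events used by sections 7.8.2 and 7.8.2.1.

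The direction follows from the wording. The size does not. The capture fractions rest on assumed uniform onset and chosen durations, the 13 to 24 h gap on assumed clock times, and the binomial figures on assumed rates. The conclusion that a real safety signal would be missed goes further than the documents allow. This should be corrected, but it does not invalidate the study.

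**What to change.** Revise item 10 and the operative diary as follows:
- Keep the waking reading on days 2 to 7.
- Add an evening, post-vaccination reading on the treatment day and an evening reading on each later day.
- Ask for a further reading whenever the participant feels feverish.
- Record the day's highest value with its time.
- State that the Table 12 fever grade is derived from the maximum post-dose value, identically in all cohorts and arms.

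The sponsor should also reconcile the 24-hour wording of the contact prompt with the reading schedule. Which contact rule applies is a clinical decision for the sponsor.

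The cost is a diary item or electronic field and one or more short entries a day; thermometers are already supplied. No visit, dose or sample size changes. There are two downsides. Reported fever rates may rise. Symptom-prompted readings depend on perception, which could differ between arms in an open-label study; the fixed evening reading limits that.

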6.4. Follow-Up for Disease History

Participants will be followed for self-reported SARS-CoV-2 exposure, symptoms of COVID-19 disease, and any outside test results for SARS-CoV-2 infection at study visits. Participants with symptoms of COVID-19 should be encouraged to seek testing and care, if appropriate, from their usual provider.

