Laboratory Assessments											

Study Period	Prescreening ^a	Baseline/ Screening	Vaccine Administration and Initial Follow-Up						Extended Follow-Up		
			1	8	22	29	36	60	180	365	
Study Day	-5 to -1	-5 to -1	1	8	22	29	36	60	180	365	
Clinic visit number	Prescreening	Screening	1	2	3	4		5	6	7	
Windows (Days)			± 3						± 7	± 14	
Chemistry panel ^h		X				X					
Hematology ⁱ		X				X					
Urinalysis ^j		X				X					
Biospecimens for SARS-CoV-2 ^k		X	X		X	X					
Collect whole blood for immunogenicity ^l			X	X					X		
Pregnancy test ^m		X	X				X				
Collect blood for SARS-CoV-2 serology	X										
HIV testing ⁿ	X										

^a If possible, the prescreening visit should occur on the same day as and immediately prior to the screening visit.

^b A TB symptom screening questionnaire per local guidelines will be used. If screening positive on questionnaire then sputum test and chest X-ray may be done to exclude the diagnosis of TB. If TB is excluded on these tests and the investigator considers that further TB testing is not clinically indicated then the potential participant may proceed with enrollment into the study. All potential participants suspected of having or with proven TB will be linked into care at their local clinic.

^c Potential exposure to SARS-CoV-2, symptoms of COVID-19, and outside testing results for SARS-CoV-2 infection will be collected at each assessment.

^d Physical examination will be performed at screening and symptom-directed (targeted) physical examination at all other time points if indicated. Height required at baseline/screening visit only.

^e Vital signs of temperature, heart rate, blood pressure, and respiratory rate will be assessed as indicated. Temperature will be documented at each visit and subsequently if clinically indicated.

^f Solicited AE diaries will be issued on day 29 and collected on day 60 only for participants in experimental arm 3 of the phase 2 study.

^g The telephone follow-up on day 36 is required only for participants in experimental arm 3 of phase 2 that get a boost on day 29.

^h See Table 9 for information on chemistry laboratory assessments.

ⁱ Hematology to include CBC with differential (5 part).

^j Urinalysis testing will include at a minimum protein, glucose, and presence of red blood cells. Sample collection should occur prior to vaccine administration.

^k Sample collection should occur prior to vaccine administration.

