APPENDIX 2. SAMPLE DIARY FOR UNSOLICITED EVENTS

STUDY NUMBER*: _____

Patient Number*	Date of Vaccine Administration	/ /	*To be completed by the site
-----------------	--------------------------------	-----	------------------------------

Please complete this diary every day beginning on the day you receive the first dose of study vaccine until 30 days after you receive the last dose of study vaccine. Each page has space for recording 7 days of information. You will be provided with enough pages to last until 30 days after you receive the last dose of study vaccine. Be sure to bring this diary each time you visit the clinic and refer to this diary when study personnel contact you by telephone for schedule safety follow up assessments.

Unsolicited AEs	Date / /						

Please describe any unusual feelings of discomfort, signs or symptoms that are not specified on the other daily diaries. If you do not experience these feelings, signs, or symptoms, please mark "no additional symptoms to report". For each separate sign and symptom you report in the diary, please note the following:
 
 • How intense it is, either Mild (no interference with activity), Moderate (some interference with activity), or Severe (significant; prevents daily activity) • How long it lasts • Any actions you took to manage the symptoms (for instance, taking medication) 							

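### Phase 1: the sample solicited diary prompts no call for a fever of 39.0°C or above lasting 24 hours or less, and does not clearly name the study site

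*Combined protocol and SAP*

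**What the plan says.** **Diary.** Under the temperature item, the Appendix 1 sample diary tells the participant: "If your temperature is 38°C for more than 24 hours, call your doctor". No other line in that diary asks the participant to contact anyone. It otherwise asks for the completed form to be brought to the next clinic visit. Temperature is entered once a day, on waking, for 7 days. Section 6.3.1 allows an electronic or a paper diary and makes reminders to complete it optional.

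**Grading.** The fever row of Table 12 (Section 7.1) has no duration criterion. The Grade 3 band reads "39.0 – 40 102.1 – 104" (°C, then °F), and anything above 40°C is Grade 4.

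**Suspension rules.** Section 7.8.2 suspends all phase 1 vaccinations on either of two conditions, both limited to events judged related to vaccine: "If 1 or more participants experience a Grade 4 AE" and "If 3 or more participants report the same or similar Grade 3 solicited AE". It also provides for event-by-event review in the first 7 days: "The SRC will also review each treatment-related SAE and toxicity, during the toxicity assessment period".

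**Scheduled contact.** Table 10 places diary training at day 1, the next clinic visit at day 8, and telephone follow-up at days 36, 180 and 365. Its footnote g limits the first of these: "The telephone follow-up on day 36 is required only for participants in experimental arm 3 of phase 2". The Appendix 2 diary asks participants to "refer to this diary when study personnel contact you by telephone for schedule safety follow up assessments", but Table 10 lists no such call in the first week.

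**The concern.** The diary prompt and the suspension rules sort fevers differently. The prompt depends on duration, and the rules depend on height. A long mild fever therefore produces a call, while a short severe one does not.

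Timing matters in phase 1 because the planned committee review of a cohort comes only after all 10 participants have finished the 7-day toxicity assessment period (Section 7.8.2.1). Until then, protection within a cohort rests on the event-driven rules and on event-by-event review, and neither can act before the site knows of the event. Section 7.1 itself says that enrolling healthy volunteers calls for very little tolerance of risk. If the site hears of a related fever above 40°C only at visit 2, a rule meant to act on a single case acts days late. A single related Grade 3 fever suspends nothing, but it is one of the three needed for the Grade 3 rule.

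The numerical suspension rules are written for phase 1. Section 7.8.3 gives phase 2 ongoing committee review without numerical triggers, so the point is made for phase 1.

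**Working it through.** The plan states no figure to reproduce here. The check sets the diary prompt against the grades and then counts days to the first scheduled contact.

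**Step 1: prompt against grade.** The prompt is read as 38°C or above for more than 24 hours. Grades come from Table 12. The fevers are illustrative.

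| Fever | Grade | Diary prompts a call? |
|---|---|---|
| 38.0°C for 25 h | 1 | Yes |
| 38.4°C for 36 h | 1 | Yes |
| 39.2°C for 30 h | 3 | Yes |
| 39.0°C for 12 h | 3 | No |
| 39.5°C for 24 h | 3 | No |
| 40.1°C for 12 h | 4 | No |
| 40.5°C for 24 h | 4 | No |

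The gap is every fever of 39.0°C or above that lasts 24 hours or less. Longer ones are caught.

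**Step 2: measurement.** With one reading a day on waking, the participant needs at least two morning readings to establish more than 24 hours. A 12-hour fever that starts after one waking reading and ends before the next is never entered unless the participant measures off schedule. So a brief fever can be reported late, or not recorded and therefore not graded.

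**Step 3: days until the site is sure to know.** Inputs:
- Visit 2 is on day 8 ± 3 (Table 10, reading the window as applying to this visit), so 8 − 3 = day 5 to 8 + 3 = day 11.
- Onset day is an assumption; day 2 is the working case.
- No contact takes place before visit 2.

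Delay = visit day − onset day.

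| Onset | Visit on day 5 | Visit on day 8 | Visit on day 11 |
|---|---|---|---|
| Day 1 | 4 | 7 | 10 |
| Day 2 | 3 | 6 | 9 |
| Day 3 | 2 | 5 | 8 |

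For a day 2 fever the delay is about 6 days, range 3 to 9. A same-day call would reduce it to 0, provided the fever is measured.

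**Step 4: other routes to the site before visit 2.**
- Observation after dosing lasts 30 minutes (Section 5.1.5).
- Reminders are optional and concern diary completion (Section 6.3.1).
- No eDiary alert is described.
- With day 36 reserved for phase 2 arm 3, the first scheduled call in phase 1 is on day 180.
- The 24-hour SAE reporting clock starts when the investigator knows of the event (Section 7.5.2).
- A visit to the participant's own doctor could become a MAAE (Section 7.2), but no deadline for that news reaching the site follows from it.

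None of these guarantees that the site hears before visit 2.

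**The case against.** The strongest reply is that the matter may already be settled elsewhere. Table 10 schedules diary training on day 1, the natural moment to tell participants when to ring the site. The consent and contact pages, not available for this review, may say so too. Appendix 1 is only a sample, and an eDiary could be watched in real time. This stands: the documents cannot show that participants receive no call-the-site instruction, and the point is conditional on that. It does not make the diary line agree with Table 12 and Section 7.8.2. If another instruction exists, participants could hold two that differ.

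A second reply is that the line is a care prompt and was never meant to feed the suspension rules. That is fair as to purpose. It is still the only contact instruction on the form the participant takes home.

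A reader might infer that the diary sends participants away from the site. The text does not settle this. The form is study-issued and speaks to the participant as from the study team, so the doctor could be the study doctor. Section 6.4 does point participants to care "from their usual provider", but that concerns COVID-19 symptoms, not fever after vaccination. The supportable statement is that the site is not clearly named.

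A reader might also infer that a number of further participants would be dosed before the site learned of a Grade 4 fever. The documents give neither a dosing pace within a cohort nor a fever rate. If all 10 are dosed on one day, the number is zero. No dose count is claimed.

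**Conclusion.** The point holds as a cheap improvement for phase 1, mainly where a paper diary is used. The diary's one contact instruction misses fevers of 39.0°C or above lasting 24 hours or less, including Grade 4 fevers, for which a single related case suspends all vaccinations. The size is a delay in notice of about 6 days (3 to 9) for a day 2 fever. That assumes the stated onset day, no earlier contact by any route, and no covering instruction in training, the eDiary or the consent and contact pages.

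It would be too strong to say that the safety data are compromised. A temperature entered in the diary still reaches the site when the form is returned, and the planned cohort review follows the full 7-day period. The part that can be lost is a brief fever falling between waking readings. No sample size or error rate is affected.

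**What to change.** In Appendix 1:
- Ask participants to take their temperature again whenever they feel feverish and to record the day's highest value. A new call threshold alone would not catch a fever that falls between waking readings.
- Ask them to call the study site the same day for any temperature of 39.0°C or above, whatever its duration, or for any entry marked severe. At present a severe entry on any other item prompts no call either.
- Keep the existing 38°C line as a care prompt.
- Match the wording to the day 1 diary training and to any call-the-site instruction on the consent or contact pages.

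The cost is a few reworded lines on a sample form and some extra participant calls to the site. The documents give no basis for estimating how many.
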